### 7.6.3 End of Study / Early Termination Visit

**Early Termination:** patients should be seen in the clinic as soon as possible after stopping study drug if they terminate the study early and refuse to enter the full Follow-Up Period.

**End of Study:** patients should be seen in the clinic 28 days ( $\pm$  3 days) after the last dose of study drug.

The following assessments are required at the End of Study/Early Termination visit:

- Limited PE, including weight, vital signs, spleen measurement and a review of body systems to assess change from previous PE
- Adverse Events and Concomitant Medications
- Blood samples for the following Local Laboratory assessments:
  - CBC with manual differential
  - Chem-12
  - C-reactive protein
- Collect MPN-SAF

## 7.7 Schedule of Events – Initial Treatment Period

INITIAL TREATMENT PERIOD		Weekly Visits ( $\pm 1$ day)										Bi-Weekly Visits ( $\pm 2$ days) a				Monthly Visits ( $\pm 3$ days) a		Follow-up ( $\pm 3$ days)	
Procedures	Screen	Day 1	Day 8 Week 1	Day 15 Week 2	Day 22 Week 3	Day 29 Week 4	Day 36 Week 5	Day 43 Week 6	Day 50 Week 7	Day 57 Week 8	Day 71 Week 10	Day 85 k Week 12	Day 99 Week 14	Day 113 k Week 16	Day 141 k Week 20	Day 169 or EOT Week 24	Pre-EOS	EOS/ET	
Informed Consent	1																		
Inclusion/Exclusion	1																		
Demographics	1																		
Physical Exam g	1	1	1	1	1	1	1	1	1	1	1k	1	1k	1k	1	1	1		
MPN-SAF h	1	1	1	1	1	1	1	1	1	1	1	1	1	1	1	1	1		
Adverse Events	1	1	1	1	1	1	1	1	1	1	1	1	1	1	1	1	1		
Concomitant Medications	1	1	1	1	1	1	1	1	1	1	1	1	1	1	1	1	1		
ECOG	1										1					1			
Bone Marrow Biopsy and Aspirate (and pathology) i	1															1c	1d		
Titration Assessment			1j	1j	1j	1j	1j	1j	1j	1j	1j	1j	1j	1j	1j				
Qualification Assessment																	1d		
Dispense IMG-7289	1	1f	1f	1f	1f	1	1	1	1	1	1	1	1	1	1				
Administer IMG-7289		←													→				
Clinical Laboratory																			
CBC with manual Diff	1	1	1	1	1	1	1	1	1	1	1	1	1	1	1	1	1		
Chem-12 (CMP)	1	1				1				1		1		1	1	1	1		
C-reactive protein	1	1				1				1		1		1	1	1	1		
Testing of mutant allele burden in granulocytes	1															1			
PT/INR/aPTT	1																		
Pregnancy Test- Serum b	1	1																	

Data collection may begin after subject has consented to participation; % NCI-CTCAE v5.0 will be used to document adverse events. Adverse events should only be collected starting on Day 1 of treatment.

- a: It is anticipated that by Week 8 all patients will have achieved a stable dose, with weekly visits no longer required. For safety purposes, weekly (or bi-weekly, as appropriate) visits may continue to be implemented at PI's discretion, if necessary. CBC with manual diff only is required at weekly visits; at bi-weekly visits, titration assessment is also required.
- b: Serum pregnancy test for women of childbearing potential (women who are not post-menopausal for 1 year or more) also performed if pregnancy suspected while patient remains on-study.
- c: Optional not required .
- d: Assess whether patient is deriving clinical benefit and safely tolerating IMG-7289, thereby qualifying for entry into the ATP upon completion of the Day 169 visit.
- e: All physical exams done after screening will be a limited PE
- f: Up-titrations are not permitted at these visits. Please see 'j' below for additional details.
- g: Spleen measurements should be taken during physical exam
- h: MPN-SAF completed once per week from Day 1 through End of Study. Provide multiple questionnaires to patient for completion during weeks there are no clinic visits.
- i: Additional aspirate to be collected and stored for potential single-cell metabolism, inflammatory signaling, or other future studies.
- j: Up-titrations may begin at ITP Day 29 and occur no more frequently than every 4 weeks from the previous up- or down-titration. Down-titrations can be made at any time in the best interest of the patient. Patients requiring a Dose Hold according to the Titration and Re-challenge Rules, or due to an (S)AE, should be monitored at least weekly for safety purposes and to enable re-challenge to commence as soon as counts return to the required level, if it safe to do so. During these visits, patients are required to undergo complete blood counts only.

k: Visit may be conducted utilizing telemedicine/video visit if deemed appropriate by PI. Limited PE, weight, VS, spleen measurement assessments will be omitted if this option is utilized.

## 7.8 Schedule of Events – Additional Treatment Period

ADDITIONAL TREATMENT PERIOD	Monthly Visits ( $\pm 3$ days) a			Suspected Relapse	Follow-up ( $\pm 3$ days)		
	Procedures	Days 1, 29 i , 57, 85 i , 113 Weeks 1, 4, 8, 12, 16	Day 141 i Week 20	Day 169 or EOT Week 24	Pre-EOS (EOT + 14 days)	EOS (Pre-EOS +14 days)/ET	
Physical Exam d	1 i	1 i	1	1	1	1	1
MPN-SAF e	1	1	1	1	1	1	1
Adverse Events	1	1	1	1	1	1	1
Concomitant Medications	1	1	1	1	1	1	1
ECOG			1	1			1
Bone Marrow Biopsy and Aspirate (and pathology) f				1 h			
Titration Assessment	1 g	1 g					
Qualification Assessment				1 c			
Dispensation of IMG-7289	1	1					
Administration of IMG-7289							
Clinical Laboratory							
CBC with manual Diff	1	1	1	1	1	1	1
Chem-12 (CMP)	1	1	1	1	1	1	1
C-reactive protein	1	1	1	1	1	1	1
Testing of mutant allele burden in granulocytes					1		

Data collection may begin after subject has consented to participation; % NCI-CTCAE v5.0 will be used to document adverse events. Adverse events should only be collected starting on day 1 of treatment

- a: It is anticipated that all patients continuing in the Additional Treatment Period will have achieved a stable dose, with bi-weekly visits no longer required. For safety purposes, bi-weekly visits may be implemented at the PI's discretion, if necessary. CBC with manual diff and titration assessment are required.
- b: Only if not performed in the prior 5 weeks.
- c: Assess whether patient is deriving clinical benefit and safely tolerating IMG-7289, thereby qualifying for entry into the ATP upon completion of the Day 169 visit.
- d: Spleen measurements should be taken during physical exam
- e: MPN-SAF completed once per week from Day 1 through End of Study. Provide multiple questionnaires to patient for completion during weeks there are no clinic visits.
- f: Additional aspirate to be collected and stored for potential single-cell metabolism, inflammatory signaling, or other future studies.
- g: Up-titration may occur no more frequently than every 4 weeks from the previous up- or down-titration. Down-titration can be made at any time in the best interest of the patient. Patients requiring a Dose Hold according to the Titration and Re-challenge Rules, or due to an (S)AE, should be monitored at least weekly for safety purposes and to enable re-challenge to commence as soon as counts return to the required level, if it safe to do so. During these visits, patients are required to undergo complete blood counts only.
- h: Optional every other Day 169 (i.e., ATP2 Day 169, ATP 4 Day 169) for as long as the patient continues to qualify for treatment.
- i: Visit may be conducted utilizing telemedicine/video visit if deemed appropriate by PI. Limited PE, weight, VS, spleen measurement assessments will be omitted if this option is utilized

## 8 Study Design/Data Collection

**Study Design:** This study will follow a Simon two-stage design with an anticipated lower limit response rate of 10% and a target response rate of >40%. With these parameters, the optimal Simon design with  $\alpha=0.05$  and 90% power would need 9 patients in the first stage and 11 patients in the second stage. After testing oral IMG-7289 on 9 patients in the first stage, the trial will be terminated if 1 or fewer respond. If the trial goes to the second stage, a total of 20 patients will be enrolled. If the total number responding is less than or equal to 4, oral IMG-7289 will be rejected; if the total number responding is more than 4, oral IMG-7289 will be considered worthy of further study.

**Engagement Approach:** Enrollment will be via MPN Hematology investigators the Mays Cancer Center ([name]) as well as by members of the Mays Cancer Center hematology team.

**Study Population and Setting:** See previous section for eligibility criteria. This investigation will identify, recruit, enroll and treat through MPN investigators the Mays Cancer Center.

**Intervention:** Participants will be initiated on a daily oral dose of 0.6 mg/kg/day of IMG-7289. Dose escalation and de-escalation algorithms will be similar to the IMG-7289 CTP-102 protocol for MF targeting a platelet count of 200 to  $400 \times 10^9/L$ .

**Outcomes:** Outcomes for Aims 1 - 2 will be collected pre- and post-intervention.

**Duration:** Study participants will be initially be treated in the study for 24 weeks. If participants are deriving clinical benefit from IMG-7289, the drug can be continued for an additional 24 weeks; this is an iterative process and may repeat indefinitely.

**Prior Relevant Experience:** Our team has extensive experience recruiting and retaining study participants in clinical trials. The Mays Cancer Center at UT Health SA is an NCI designated cancer center widely recognized for Phase I clinical trials and drug development discovery. [name] will be the study PI and was formerly Deputy Director of the Cancer Center at Mayo Arizona and continues to collaborate closely between both institutions. [name] has worked investigating QOL and symptom burden in MPNs since 2010. [name] is the project biostatistician and has over 40 years' experience in the analysis and reporting of clinical and epidemiological studies.

## 9 Minority Accrual

### 9.1 Purpose

To assist the Principal Investigators (PIs) conducting Investigator Initiated Trials (IIT) in determining whether or not they are meeting the NIH and NCI guidelines and recommendations for the inclusion of minorities in Clinical Trials.

#### Preliminary information that Principal Investigators should consider include:

- Overall Representation of Minorities in the target catchment area
- The ethnic/racial distribution of the specific type of cancer that is being targeted

The following resources can be utilized to determine target sample sizes for ethnic groups:

- Texas Health Data <http://soupfin.tdh.state.tx.us/txhd.htm>
- Texas Cancer Registry [www.dshs.state.tx.us/tcr/](http://www.dshs.state.tx.us/tcr/)
- SEER Cancer Statistics Review [www.seer.cancer.gov](http://www.seer.cancer.gov)
- ACS Cancer Statistics [www.cancer.org](http://www.cancer.org)

#### **\*Estimated Target Accrual (Total)**

This section asks for a **projection** of the total ethnic/racial and gender mix of the subjects

**Breakdown of subjects - Indicate the total targeted/planned accrual by Race & Gender**

Race	% Male	% Female
Black or African American	10	10
American Indian or Alaskan Native	0	0
Asian	0	0
Native Hawaiian or Other Pacific Islander	0	0
White	30	30
More Than One Race (Multiracial)	60	60
Total	100	100

**Breakdown of subjects - Indicate the total targeted/planned accrual by Ethnicity & Gender.**

Ethnicity	% Male	% Female
Hispanic or Latino	10	10
Not Hispanic or Latino	40	40
Total	50	50

## Section 2: Clinical Investigator Tools for Recruitment of Minorities

Tool included in study	LIST OF TOOLS AND ACTIONS FOR INCREASING MINORITY ACCRUAL TO CLINICAL TRIALS For assistance with submitting IRB documents, developing materials in English and Spanish, and scheduling public service announcements, please contact [contact]
Yes  No 	1. Include Clinical Trial information on Mays Cancer Center website in both English and Spanish ( Please notify [contact] ).
Yes  No 	2. Use of Bilingual Research Team Member or Translation services
Yes  No 	3. Identification of bilingual Patient Navigator representative of the Target Population Please Specify: 
Yes  No 	4. Informed Consent available in Spanish
Yes  No 	6. Information Brochures in English and Spanish** ( IRB approval required )
Yes  No 	7. Flyers in English and Spanish (two sided, printed in English on one side and Spanish on the other).** ( IRB approval required )
Yes  No 	8. Public Service Announcements (PSAs) or Advertisements- Spanish Radio** ( IRB approval required )
Yes  No 	9. PSA's or Advertisements -Spanish newspapers (e.g., La Prensa)** ( IRB approval required )
Yes  No 	10. PSA's or Advertisements -Spanish Television (e.g., Univision)** ( IRB approval required )
Yes  No 	11. Patient Friendly Fast Facts in English and Spanish ** ( IRB approval required )
Yes  No 	12. Outreach to advocacy or community organizations (including presentations or awareness campaigns). Please specify:  

We will contact MPN- Research Foundation, MPN forum, and other MPN Specific resources to advertise this study. These websites do not target any Specific Hispanic or latino populations.

Yes  No 	13. Other. Please Specify: 

\*\* - It is recommended to submit any patient materials to the IRB as an amendment after the initial IRB approval has been granted

Translational Research Component

Translational components of the study include the analysis of bone marrow histology.

## 10 Statistical Analysis

**Analytic Plan:** This will be a one arm Simon 2-stage design with up to N=20 subjects. Complete hematologic remission (primary outcome) and overall symptom burden (secondary outcomes) will be assessed at weeks 20 and 24 (response at Week 24 only).

**Sample Size and Power:** This study will follow a Simon two-stage design with an anticipated lower limit response rate of 10% and a target response rate of >40%. With these parameters, the optimal Simon design with  $\alpha=0.05$  and 90% power would need 9 patients in the first stage and 11 patients in the second stage. After testing oral IMG-7289 on 9 patients in the first stage, the trial will be terminated if 1 or fewer respond. If the trial goes to the second stage, a total of 20 patients will be enrolled. If the total number responding is less than or equal to 4, oral IMG-7289 will be rejected; if the total number responding is more than 4, oral IMG-7289 will be considered worthy of further study.

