Taking this observation into account in association with the therapeutic goal for the treatment of myeloproliferative neoplasms -- inhibiting LSD1 activity in hematopoietic cells for only a fraction of the 24-hour dosing cycle -- and PK modeling, the original starting dose in the CTP-102 protocol for myelofibrosis patients was 0.25 mg/kg/d. Platelet counts in the first twenty patients ranged from 102 to 1039 k/ $\mu$ L and all required a dose increase to lower platelet counts. In a recent analysis of the ongoing IMG-7289-CTP-102 study in myelofibrosis patients, the daily dose of IMG-7289 needed by a majority of patients to achieve a platelet count in the target range (50-75 k/ $\mu$ L) ranged between 0.6 to 0.8 mg/kg/d with the full dosing spectrum of 0.4-1.5 mg/kg. The dose needed to reduce the platelet count to the target range in patients with myelofibrosis was *not* correlated with the starting platelet count or the antecedent hematologic history. Platelet counts in patients with ET will, on average, be significantly higher than those in patients with myelofibrosis who have failed treatment with the standard of care. Notwithstanding, the kinetics of changes in platelet counts in patients with ET treated with IMG-7289 are expected to be similar to those patients with myelofibrosis. Accordingly, to enable ET patients to reach the optimum dose sufficient to reduce platelets below 400 k/ $\mu$ L while still maintaining an adequate safety margin, an IMG-7289 starting dose of 0.6 mg/kg QD has been selected.

Collectively, these studies established some key points. First, inhibition of LSD1 for a fraction of the 24-hour dosing cycle can be achieved safely. Second, the platelet count can be targeted to a specific range by adjusting the dose of IMG-7289.

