### 4.2 Endpoints

#### 4.2.1 Primary Endpoint

- Determine the proportion of patients who achieve complete hematologic remission at Week 24 using ELN response criteria for ET ([Barosi et al., 2013](#)), as per protocol appendix 12.4.

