#### 5.2 Initial Treatment Period

Using dose titration, the dose of IMG-7289 will be adjusted in each patient to that dose that provides sufficient exposure to safely inhibit thrombopoiesis for a fraction of the dosing cycle (designated as the  $D_{pi}$ ). Treatment will begin on Day 1 at the IMG-7289  $D_s$  of 0.6 mg/kg QD for all patients, with dose-titration contingent on the comparison of hematology values from the prior visit. Up-titration may begin on ITP Day 29 and occur no more frequently than every 4 weeks from the previous up- or down-titration. Down-titration can be made at any time in the best interest of the patient. Up-titration will be made in increments of 0.2 mg/kg/d, and down-titration in decrements of 0.1 or 0.15 mg/kg/d.

The dose of IMG-7289 needed to reduce platelets to the target range is anticipated to be up to approximately 2 mg/kg QD; however, this is not the upper limit for titration purposes as the dose needed to achieve a therapeutic effect will vary among patients and may change over time. The platelet titration target expected to be associated with a clinically significant therapeutic effect is:  $\geq 200$  to  $\leq 400$  k/ $\mu$ L (200-400 x  $10^9$ /L).

During the ITP, patients will initially return for study assessments weekly for the first 8 weeks (ITP Days 8, 15, 22, 29, 36, 43, 50 and 57), at least bi-weekly for 8 weeks (ITP Days 71, 85, 99 and 113) and then monthly for 8 weeks (ITP Days 141 and 169). It is anticipated that by Week 8 (Day 57) patients will have achieved a stable dose, with weekly visits no longer necessary. For safety purposes, weekly visits may continue at the PI's discretion (note: bi-weekly visits may also continue post Day 113), if necessary. On Day 169 bone marrow sampling is required. At the Day 169 visit, a 'qualification' assessment will be made to determine whether the patient is deriving clinical benefit and safely tolerating IMG-7289. Such patients qualify for entry into the ATP, a transition which should occur without interruption in dosing. Patients not deriving clinical benefit, or who achieve complete remission (CR) or partial remission (PR) and subsequently relapse (Section 12.4) the equivalent of treatment failures, will discontinue IMG-7289 and undergo End of Treatment (EoT), pre-End of Study (pre-EoS) and End of Study (EoS) visits.

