### **7.3.3 ITP Bi-Weekly Visits - Days 71, 85, 99 and 113 ( $\pm$ 2 days\*)**

**\*Important:** The  $\pm$ 2 day visit window applies to the visit (e.g., 'Day 71' visit may be conducted on Day 69, Day 70, Day 71, Day 72 or Day 73 as dictated by site and patient schedule), and not to individual assessments, unless otherwise noted for a specific assessment. To clarify, the expectation is that all required assessments will be done on a single visit day with the exception of those specifically noted below.

**Note:** It is anticipated that by Week 8 patients will have achieved a stable dose, with weekly visits no longer necessary. For the exceptional patient whose dose has not stabilized, weekly visits may continue at the PI's discretion. For such patients, the following is required at each weekly visit:

- Pre-dose: Blood samples for the following Local Laboratory assessments:
  - CBC with manual differential and hematology assessment to determine if dose titration is required\*\* (note: up-titrations may occur no more frequently than every 4 weeks from the previous up- or down-titration; down-titrations may occur at any time in the best interest of the patient)

*Important:* may be performed up to 2 days ahead of the main visit to avoid the need for IMG-7289 dispensation on the day of blood sampling. For example, if a visit is scheduled on a Wednesday, the hematology panel and associated titration assessment can be performed Monday or Tuesday, if needed, to ensure IMG-7289 is dispensed and available for collection at the Wednesday visit.

All other patients will undergo the following at bi-weekly visits:

- Limited PE\*, including weight\*, vital signs\*, spleen measurement\* and a review of body systems to assess change from previous PE
  - (\*) assessments may be omitted on Days 71 and 99 as these visits may be conducted utilizing telemedicine/video visit option at PI discretion.
- Adverse Events and Concomitant Medications
- Pre-dose: Blood samples for the following Local Laboratory assessments:

- CBC with manual differential and hematology assessment to determine if dose titration is required\*\* (note: up-titrations may occur no more frequently than every 4 weeks from the previous up- or down-titration; down-titrations may occur at any time in the best interest of the patient)

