## 12.4 ELN Response Criteria for ET (Barosi *et al*, 2013)

Response Categories	Criteria
Complete Remission	
A	Durable* resolution of disease-related signs including palpable hepatosplenomegaly, large symptoms improvement, † AND
B	Durable* peripheral blood count remission, defined as: platelet count $\leq 400 \times 10^9/L$ , WBC count $< 10 \times 10^9/L$ , absence of leukoerythroblastosis, AND
C	Without signs of progressive disease, and absence of any hemorrhagic or thrombotic events, AND
D	Bone marrow histological remission defined as disappearance of megakaryocyte hyperplasia and absence of >grade 1 reticulin fibrosis.
Partial Remission	
A	Durable* resolution of disease-related signs including palpable hepatosplenomegaly, and large symptoms improvement, AND
B	Durable* peripheral blood count remission, defined as: platelet count $\leq 400 \times 10^9/L$ , WBC count $< 10 \times 10^9/L$ , absence of leukoerythroblastosis, AND
C	Without signs of progressive disease, and absence of any hemorrhagic or thrombotic events, AND
D	Without bone marrow histological remission, defined as the persistence of megakaryocyte hyperplasia.
No Response	Any response that does not satisfy partial remission
Progressive Disease	Transformation into PV, post-ET myelofibrosis, myelodysplastic syndrome or acute leukemia‡

Molecular response is not required for assignment as complete response or partial response. Molecular response evaluation requires analysis in peripheral blood granulocytes. Complete response is defined as eradication of a preexisting abnormality. Partial response applies only to patients with at least 20% mutant allele burden at baseline. Partial response is defined as <math>\geq 50\%</math> decrease in allele burden.
 
WBC, white blood cell.
 
*Lasting at least 12 wk.
 
†Large symptom improvement (<math>\geq 10</math>-point decrease) in MPN-SAF TSS.
 
‡For the diagnosis of PV see World Health Organization criteria (WHO); for the diagnosis of post-ET myelofibrosis, see the IWG-MRT criteria; for the diagnosis of myelodysplastic syndrome and acute leukemia, see WHO criteria.
	

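### Section 10 assesses the primary outcome at Weeks 20 and 24, visits that cannot show the 12 weeks of durability required by Appendix 12.4, and no section names the visits that do

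*Combined protocol and SAP*

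**What the plan says.** Three places define or time the primary outcome.

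- Section 4.2.1 sets the endpoint: "Determine the proportion of patients who achieve complete hematologic remission at Week 24 using ELN response criteria for ET", with a pointer to Appendix 12.4.
- Appendix 12.4 makes criterion A (signs and symptoms) and criterion B (blood counts) durable, and its footnote defines durable as "Lasting at least 12 wk". Criteria C (no progression, bleeding or thrombosis) and D (marrow histology) carry no duration.
- Section 10, the only analysis text, says: "Complete hematologic remission (primary outcome) and overall symptom burden (secondary outcomes) will be assessed at weeks 20 and 24 (response at Week 24 only".

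Section 8 adds only that outcomes are collected before and after the intervention. No section says which visits establish the 12 weeks, or how a missing assessment counts.

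The same response count drives the Simon rule in Sections 8 and 10: stop after 9 patients with 1 or fewer responders, and reject the drug with 4 or fewer of 20. Section 11 sends the 9-patient result to the DSMB before 11 more patients are enrolled.

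**The concern.** The analysis section names two visits four weeks apart for an endpoint that needs twelve. One analyst may score on the visits that Section 10 names. Another may look back 12 weeks, as Appendix 12.4 requires. They would disagree on a patient whose remission is first seen at Day 141 and still holds at Day 169: a responder to the first and not an ELN complete remission to the second.

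The trial is small enough for one such patient to matter. The stage 1 decision separates 1 from 2 responders among 9, and the final decision separates 4 from 5 among 20. If shorter remissions are counted, the chance of calling the drug worthy of further study, judged against true ELN complete remission, is higher than the design intends. If instead the 40% target was set with shorter remissions in mind, enforcing 12 weeks costs power. The plan does not say which definition the 10% and 40% rates describe.

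**Working it through.** **1. The plan's own figure.** Inputs from Section 10: p0 = 0.10, p1 = 0.40, stop if ≤1 of 9, reject if ≤4 of 20.

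P(declare worthy | p) = Σ over x = 2 to 9 of P(X1 = x) × P(X2 ≥ 5 − x), with X1 ~ Bin(9, p) and X2 ~ Bin(11, p).

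At p = 0.10:

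| Stage 1 responders | P(X1 = x) | P(X2 ≥ 5 − x) | Product |
|---|---|---|---|
| 2 | 0.1722 | 0.0896 | 0.0154 |
| 3 | 0.0446 | 0.3026 | 0.0135 |
| 4 | 0.0074 | 0.6862 | 0.0051 |
| 5 or more | 0.0009 | 1 | 0.0009 |

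The sum is 0.0349. At p = 0.40 the same sum is 0.902. A search over two-stage designs returns 9 and 20 patients with cut-offs 1 and 4 as the optimal design for error ≤0.05 and power ≥0.90. The sample-size statement is therefore correct and not in dispute.

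**2. Span of the visits Section 10 names.** Week 20 is Day 141 and Week 24 is Day 169 (Section 7.7). Both have a window of ±3 days, and the blood count may be drawn up to 2 days early (Section 7.3.4).

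- Nominal: 169 − 141 = 28 days.
- Visit windows: (169 − 3) − (141 + 3) = 22 to (169 + 3) − (141 − 3) = 34 days.
- Blood count with early draw: (169 − 3 − 2) − (141 + 3) = 20 to (169 + 3) − (141 − 3 − 2) = 36 days.
- Required: 12 × 7 = 84 days. Even the longest span is 84 − 36 = 48 days short.

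**3. Visits that could show 12 weeks.** The latest qualifying start is 169 − 84 = Day 85, a scheduled visit with a ±2-day window. Day 99 gives 70 days and Day 113 gives 56. Blood counts are scheduled at Days 85, 99, 113, 141 and 169, and the MPN-SAF is completed weekly, so the look-back needs no new counts or forms. Spleen data are sparser. Section 7.3.3 says that the starred items, which include the spleen, "assessments may be omitted on Days 71 and 99 as these visits may be conducted utilizing telemedicine/video visit option at PI discretion"; Section 7.3.4 allows the same on Day 141. In-person spleen measurements therefore remain at Days 85, 113 and 169.

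Counting in nominal days accepts an actual blood-count span of (169 − 3 − 2) − (85 + 2) = 77 to (169 + 3) − (85 − 2 − 2) = 91 days.

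**4. Sensitivity of the error (assumption only).** Let s be the share of Week 20/24 responders who lack 12 weeks, and assume that every 12-week responder is also a Week 20/24 responder. If true ELN complete remission is 10%, the Week 20/24 rate is 0.10 / (1 − s).

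- s = 0: rate 10.0%, P(declare worthy) = 3.5%.
- s = 10%: rate 0.10 / 0.90 = 11.1%, P(declare worthy) = 5.1%.
- P(declare worthy) reaches 5.0% at a rate of 11.03%, so s = 1 − 0.10 / 0.1103 = 0.093, about 9%.

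The documents give no value for s.

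**5. Sensitivity of power (assumption only).** If 40% describes a shorter remission and the 12-week rate is 30%, P(declare worthy) at p = 0.30 is 0.69 instead of 0.90.

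**The case against.** The best defence is that Section 10 fixes when response is scored, not what data are used. It restricts response to Week 24 and does not make Week 20 a confirmation visit. It offers no definition of remission of its own, so the analyst must go to Appendix 12.4 and meet the 12 weeks there. The look-back data exist. On that reading the error stays at 3.5% and all that is missing is a list of visits.

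Much of this stands. A reader might infer that Section 10 replaces the durability requirement with a four-week one; the text does not say so. But the defence has to supply a look-back that no section states, and it leaves the mention of Week 20 without a purpose. Even with Appendix 12.4 applied, the start visit and the handling of missing assessments are open.

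Three stronger inferences should not be drawn.

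- **That late responders will be common because titration is slow.** Section 5.2 says "Up-titration may begin on ITP Day 29 and occur no more frequently than every 4 weeks from the previous up- or down-titration", and "The dose of IMG-7289 needed to reduce platelets to the target range is anticipated to be up to approximately 2 mg/kg QD". It also says "It is anticipated that by Week 8 (Day 57) patients will have achieved a stable dose, with weekly visits no longer necessary", while Section 3.4 reports that the dose most myelofibrosis patients needed "ranged between 0.6 to 0.8 mg/kg/d with the full dosing spectrum of 0.4-1.5 mg/kg". The documents point both ways and allow the PI to depart from the titration table, so this settles nothing.
- **That the error is grossly inflated.** Large values of s give large errors, but no value has a source. A discordant patient would have to meet every other part of Appendix 12.4, including marrow remission and a symptom-score fall of at least 10 points, and fail on duration alone.
- **That spleen may be missing at Day 85 because of video visits.** The extracted header of Section 7.7 seems to put the video footnote on Day 85. The Physical Exam row of that table marks Days 71 and 99 but not Day 85, in line with Section 7.3.3. The Version 13 summary keeps Days 85, 113 and 169 in person, and Section 7 makes its own text the main guidance.

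**Conclusion.** The point holds as a conflict in the scoring rule for the primary endpoint, and it should be fixed. The visits named in Section 10 span 28 days, at most 36 for blood counts, against 84 required, and no section names others. That part rests on the protocol's own days and windows and needs no assumption.

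The effect on the decision is possible but cannot be sized from the documents. One patient counted on a remission of about four weeks can move the trial across either cut-off. The 9% threshold rests on a true ELN rate of exactly 10% and on every 12-week responder also being a Week 20/24 responder. The power figure of 0.69 rests on an assumed 12-week rate of 30%. Neither is a forecast. If Appendix 12.4 is applied in full, the design's exact error is 3.5%, within the stated 5%.

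**What to change.** Replace the Section 10 sentence with wording such as:

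> Response is scored at Week 24 by Appendix 12.4. Criteria A and B must be met at the scheduled assessments from Day 85 through Day 169, counted in nominal visit days, with spleen judged at in-person visits. A patient without evaluable Day 85 and Day 169 assessments is a non-responder.

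State that the 10% and 40% rates refer to this 12-week definition. Date the rule. If the 9-patient interim has already been scored, report both the Week 20/24 count and the 12-week count for those patients, because the rule would then have been fixed after their results were known.

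The sponsor should also say how an out-of-range or missing intermediate visit counts and whether off-week symptom forms are used. The documents compel no particular answer.

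**Cost.** No new visits or data are needed, and the sample size is unchanged. The observed response rate and the power may be lower than under a shorter definition. Nominal counting accepts an actual blood-count span of 77 to 91 days, so some patients will qualify on slightly less than 84 days. In an open-label trial already at Version 13, the date of the rule needs to be visible in the report.
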